3.0 Protocol Summary

Title:	Safety of Oral Anticoagulation Therapy Withdrawal after Successful Cardiac Ablation in Patients with Atrial Fibrillation and Associated High Risk Factors for Embolic Events (OAT Pilot Study)
Design:	Prospective, multicenter, randomized (1:1), controlled, two-arm unblinded study.
	Patients undergoing successful cardiac ablation for atrial fibrillation who remain AF recurrence-free 3 months after successful ablation and continue to meet the inclusion/exclusion criteria will be screened for enrollment in the trial. After fulfilling all of the inclusion/exclusion criteria, patients who consent to participate in the study and remain AF recurrence-free will be randomized to one of two study arms: (1) OAT Withdrawal (Test) Group or (2) OAT (Control) Group and participate in the Evaluation Period (12 months).
Objective:	The objective of this study is to determine the safety of discontinuing oral anticoagulation therapy in high risk patients who have had a successful cardiac ablation and remain AF recurrence free for 3 months post ablation.
Hypothesis:	High risk subjects who have successful cardiac ablation and remain free from AF recurrence for 3 months post ablation procedure can discontinue their OAT without an increased risk of thromboembolic events as compared to those who remain on OAT.
Enrollment:	Up to 100 subjects will be enrolled in this study.
Clinical Sites:	Up to 10 sites in the United States and Europe will be included.
Subject Population:	Patients who have undergone successful cardiac ablation for AF that are 3months post procedure and remain free from AF recurrence.
	Eligible patients who sign the study informed consent form will be randomized (1:1) into one of two study arms:
	
• OAT Withdrawal (Test) Group: discontinue OAT during the Evaluation Period• OAT (Control) Group: continue OAT during the Evaluation Period
Inclusion/Exclusion Criteria:	Inclusion Criteria: 
1. Successful cardiac ablation for AF2. Documented freedom from AF recurrence (symptomatic or asymptomatic arrhythmic recurrences lasting longer than 30 seconds) 3 months after successful cardiac ablation (AF recurrence during 3-month blanking period is excluded).3. Patient must have been on a commercially approved anticoagulation therapy for at least two (2) months prior to randomization in the OAT Study. Commonly prescribed Oral Anticoagulation and Antiplatelet therapies for use in this study are listed in Appendix A. For patients enrolled in Germany,

only those who are prescribed therapies listed in Appendix A can be enrolled in this study.

4. CHADS₂ score ≥ 2 or CHA₂DS₂-VASc score ≥ 3
5. Left ventricular ejection fraction $> 25\%$
6. LA size ≤ 65
7. High risk for thromboembolic events (i.e., CHADS₂ score ≥ 2 or CHA₂DS₂-VASc score ≥ 3 and require OAT before undergoing cardiac ablation)
8. Able and willing to comply with all pre- and follow-up testing and requirements
9. Signed informed consent form
10. Age 18 years or older

Exclusion Criteria:

1. OAT required for reasons not related to AF (i.e., prosthetic valve, PV stenosis, previous pulmonary embolism, presence of spontaneous echo contrast [SEC] at standard echo performed at 3-months follow-up).
2. Any cardiac surgery within the past 60 days (2 months) or valvular cardiac surgical procedure at any time (i.e., ventriculotomy, atriotomy, and valve repair or replacement and presence of a prosthetic valve)
3. Previous myocardial infarction (MI), or a percutaneous coronary intervention PCI within the past 3 months
4. Awaiting cardiac transplantation or other cardiac surgery within the next 365 days (12 months)
5. Documented left atrial thrombus
6. Significant pulmonary disease, (e.g., restrictive pulmonary disease, constrictive or COPD) or any other disease or malfunction of the lungs or respiratory system that produces chronic symptoms
7. Significant medical problem that in the opinion of the investigator would preclude enrollment in this study
8. Women who are pregnant (as evidenced by pregnancy test if pre-menopausal)
9. Acute illness or active systemic infection or sepsis
10. Unstable angina
11. Contraindication to anticoagulation (i.e., heparin, warfarin or another commercially available anticoagulation medication)
12. History of blood clotting or bleeding abnormalities
13. Life expectancy less than 360 days (12 months)
14. Uncontrolled Heart Failure or NYHA Class III or IV heart failure
15. Enrollment in a clinical study evaluating another device or drug, within the past 6 months
16. Unable or unwilling to comply with protocol requirements

Endpoints:

Primary

Composite endpoint represented by the occurrence of any major thromboembolic event (stroke [i.e., ischemic, hemorrhagic or cryptogenic] that is an acute onset of a focal neurologic deficit of presumed vascular origin lasting for ≥ 24 hours or resulting in death) or major hemorrhagic complication (major bleeding) during the 12-month Evaluation Period.

Secondary:

- Minor bleeds
- Hospitalization with any thromboembolic or major hemorrhagic event
- All cause mortality
- QoL (SF-36)
- AF recurrence
- Repeat ablation for AF

Study Duration: 2 years (1 year enrollment period and 1 year follow-up)

4.0 Acronyms/Abbreviations and Study Definitions

Table 1. Acronyms and Abbreviations Used in the Study Protocol

Acronym / Abbreviation	Expanded Term
AAD	AntiArrhythmic Drug
ACC/AHA	American College of Cardiology/American Heart Association
ADR	Adverse Drug Reaction
AE	Adverse Event
AF	Atrial Fibrillation
COPD	Chronic Obstructive Pulmonary Disease
CRF	Case Report Form
CRO	Contract Research Organization
CT	Computed tomography
EB	Ethics Board
EC	Ethics Committee
ECG	Electrocardiogram
eCRF	Electronic Case Report Form
EP	Electrophysiology
FDA	Food and Drug Administration
GCP	Good Clinical Practices
GI	Gastrointestinal
HM	Holter Monitor
ILR	Implantable Loop Recorder
HRS	Heart Rhythm Society
ICF	Informed Consent Form
INR	International Normalized Ratio
IRB	Institutional Review Board
LA	Left Atrium
LAA	Left Atrial Appendage
LV	Left Ventricle
LVEF	Left Ventricular Ejection Fraction
MI	Myocardial Infarction
MRI	Magnetic Resonance Imaging
NYHA	New York Heart Association
OAT	Oral Anticoagulation Therapy
PAC	Physician Advisory Committee
PI	Principal Investigator
PLAX	Parasternal Long Axis
PV	Pulmonary Vein
PVAI	Pulmonary Vein Antrum Isolation
QoL	Quality of Life
RA	Right Atrium
RFCA	Radiofrequency Catheter Ablation
RV	Right Ventricle
SAE	Serious Adverse Event
SEC	Spontaneous Echo Contrast
SMC	Safety Monitoring Committee
SOC	Standard of Care
SOP	Standard Operating Procedure
SR	Sinus Rhythm
TEE	Transesophageal Echocardiography
TIA	Transient Ischemic Attack
TTE	Transthoracic Echocardiography

Table 2. Study Definitions

Term	Definition
AF Recurrence	Recurrence of an AF episode, which is an episode of AF ≥ 30 seconds in duration. Atrial fibrillation and atrial flutter (including atypical flutter) are considered episodes of AF.
Asymptomatic (Silent) AF	Documented by ECG without subject symptoms.
Documented AF Episode	Documentation obtained with an arrhythmia monitoring tool. This may include ECG, TTM, HM, or telemetry strip. Reporting of a symptomatic episode by subjects is not considered as a documented episode.
High-burden Paroxysmal AF	AF episodes that last less than 30 days. Episodes may terminate spontaneously or via cardioversion.
High-risk	CHADS ₂ score ≥ 2 or CHA ₂ DS ₂ -VASc score ≥ 3
Long Standing Persistent AF	Longstanding persistent AF is defined as continuous AF of >12 months duration.
Major hemorrhagic complication	
 • Stroke is an acute onset of a focal neurologic deficit of presumed vascular origin lasting for ≥ 24 hours or resulting in death. 
 ◦ Stroke (i.e., ischemic, hemorrhagic or cryptogenic) occurrence. Stroke is categorized as ischemic or hemorrhagic or cause unknown (based on computed tomographic or magnetic resonance imaging or autopsy). ◦ Fatal stroke is defined as death from any cause within 30 days of stroke. ◦ Severity of stroke will be assessed by modified Rankin score at discharge from hospital and at 3 to 6 months later. • Bleeding (major) is defined by ≥ 1 of the following criteria: 
 ◦ Bleeding associated with reduction in hemoglobin level of at least 2.0 g/L; ◦ leading to transfusion of at least 2 U of blood or packed cells; or ◦ symptomatic bleeding in a critical area or organ such as intraocular, intracranial, intraspinal or intramuscular with compartment syndrome, retroperitoneal bleeding, GI bleeding, intra-articular bleeding, or pericardial bleeding. • Bleeding (life-threatening) if ≥ 1 of the following criteria are met: 
 ◦ fatal, symptomatic intracranial bleed; ◦ reduction in hemoglobin level of at least 5.0 g/L; ◦ transfusion of at least 4 U of blood or packed cells; ◦ associated with hypotension requiring the use of intravenous inotropic agents; or ◦ necessitated surgical intervention.
Minor hemorrhagic event (Minor Bleeds)	Clinical bleeds that do not fulfill the criteria for major bleeds
Paroxysmal AF	Paroxysmal AF is defined as recurrent AF (≥ 2 episodes) that terminates spontaneously within 7 days. Episodes of AF of ≤ 48 h duration that are terminated with electrical or pharmacologic cardioversion should also be classified as paroxysmal AF episodes.
Permanent AF	The term permanent AF is not appropriate in the context of patients undergoing catheter or surgical ablation of AF, as it

Term	Definition
	refers to a group of patients for which a decision has been made not to restore or maintain sinus rhythm by any means, including catheter or surgical ablation. If a patient previously classified as having permanent AF is to undergo catheter or surgical ablation, the AF should be reclassified.
Persistent AF	Persistent AF is defined as continuous AF that is sustained beyond 7 days. Episodes of AF in which a decision is made to electrically or pharmacologically cardiovert the patient after ≥ 48 h of AF, but prior to 7 days, should also be classified as persistent AF episodes.
Successful Cardiac Ablation	After Cardiac Ablation, no symptomatic or asymptomatic AF recurrence ≥ 30 seconds (without increased or new AADs) following the 3-month blanking period.
Symptomatic AF	Symptom(s) which is/are exhibited by the subject, which make them seek medical attention, and are concurrent with a documented episode by ILR, ECG, TTM, HM, or telemetry recording. Symptoms may include but are not limited to: palpitations, irregular pulse (eg, rapid, racing, pounding, fluttering, bradycardia), dizziness, weakness, chest discomfort, and breathlessness.
Thromboembolic Event	Any documented clinical event due to the embolic occlusion of an artery in the brain or other organs.

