Although the efficacy of warfarin in preventing stroke in AF patients has been clearly demonstrated, oral anticoagulation is still underused in clinical practice for several reasons. Firstly, oral anticoagulation therapy carries a substantial risk of hemorrhage; this could be underestimated in clinical practice, considering the restrictive selection criteria used in randomized trials, in which patients with lower risk of bleeding are often enrolled. For example, in the SPINAF trial only 7% of the 7982 patients initially screened were enrolled.¹⁰ Moreover, the risk of hemorrhage is strictly related to the patient's age. Indeed, the incidence rate of major hemorrhage has been found to rise from 1.5 per 100 patient-years for patients younger than 60 years to 4.2 per 100 patients-years for patients older than 80 years (hazard ratio of 2.7).¹¹ In a meta-analysis of major randomized trials of oral anticoagulation therapy, the mean age of patients was 69 years, and only 20% of participants were older than 75 years.⁹

By contrast, in clinical practice this latter group of patients represents more than 50% of the population that needs to be treated with anticoagulation therapy.⁷ The second reason for the underuse of oral anticoagulation is that this therapy, specifically warfarin, is associated with restrictions in everyday life, as it requires frequent monitoring of the INR level in order to adjust the therapeutic dosage. Finally, it is well known that a considerable percentage of patients are unable to comply with oral anticoagulation therapy. In warfarin-treated patients, discontinuation of this therapy occurs at rates of up to 38% a year and approximately 50% of strokes occur during inadvertent therapeutic lapses or in subjects who temporarily or permanently cease therapy.⁸

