5.3 Risk Analysis

The risks posed during the conduct of this study are expected to be comparable to those anticipated with the use of OAT according to current AF management guidelines.^{6, 30-33} Anticoagulation therapies have been approved for many decades and the risks and complications are well known. Depending on a patient's risk factors, anticoagulation therapy is recommended for a period of time after undergoing an ablation procedure.³¹ For the OAT Pilot Study, appropriate measures have been implemented to minimize the risk to subjects, while still providing the possible benefits of the two treatment options.

Description and Analysis of Risks:

The OAT Pilot Study will assess the risks associated with subjects randomized to one of two study arms, OAT Withdrawal (Test) Group or OAT (Control) Group. No additional risks are anticipated for subjects randomized to the OAT arm of the study as these subjects will continue with their current physician-prescribed OAT. The major risk for subjects continuing OAT during the Evaluation Period is the risk of major bleeding and hemorrhagic stroke.³¹ The main risks for subjects discontinuing OAT during the Evaluation Period is the increased risk of a thromboembolic event. This risk is higher in subjects with a history or previous thromboembolism, advanced age, hypertension, diabetes mellitus and heart failure.

Minimization of Risks:

The criteria for subject selection, study methods, personnel selection, facilities, and training that have been specified in this study are intended to minimize the risk to enrolled subjects. Subjects will be carefully screened prior to study enrollment to confirm compliance with the study inclusion and exclusion criteria. In addition, prior to randomization, all patients will undergo further AF monitoring to confirm they are AF recurrence free for 3 months following catheter ablation. Once enrolled, additional AF monitoring and clinic follow-up visits are required for each subject to ensure an appropriate level of safety monitoring. Patients experiencing AF recurrence during the study will be treated per the investigator's discretion.

Additionally, safety data will be evaluated periodically during enrollment and follow-up by a physician review committee functioning as a Global Safety Monitoring Committee (GSMC) for this study.

Potential Benefit:

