10.0 Study Endpoints

10.1 Primary Endpoint

The primary endpoint is a composite endpoint represented by the occurrence of any major thromboembolic event (stroke [i.e., ischemic, hemorrhagic or cryptogenic] that is an acute onset of a focal neurologic deficit of presumed vascular origin lasting for ≥ 24 hours or resulting in death) or major hemorrhagic complication (major bleeding) during the 12-month Evaluation Period.

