13.7.2.1 Minor Hemorrhagic Events (Minor Bleeds) (%)

A minor hemorrhagic event (minor bleed) is defined as clinical bleeds that do not fulfill the criteria for major bleeds. Descriptive statistics and type of minor hemorrhagic event will be summarized and listed by randomization groups.

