15.6 Global Safety Monitoring Committee (GSMC)

All AEs will be monitored until they are resolved or explained. Each AE will be reported regardless of severity, outcome, or causality. To minimize risks to subjects enrolled in the clinical investigation, the sponsor will convene a formal Global Safety Monitoring Committee (GSMC) to review the safety data and recommend appropriate action(s) to ensure subject safety.

The GSMC is tasked with adjudicating severity and causality of adverse events. Activities related to the collection of source documentation and narrative writing for events presented for adjudication by the GSMC will be performed by the sponsor or designee. In addition to reviewing individual adverse events, the GSMC may also review the accumulated safety data for the clinical investigation. Sponsor or designee will collect and compile the information packets or listings for the GSMC to review. Biosense Webster will manage the GSMC.

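### Table 2 makes a haemoglobin fall of 2.0 g/L (0.2 g/dL) enough for major bleeding, a primary-endpoint component; the unit looks like g/L written for g/dL

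*Combined protocol and SAP*

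**What the plan says.** Table 2 (Section 4.0) defines major bleeding by three criteria, any one of which is sufficient. The first is "Bleeding associated with reduction in hemoglobin level of at least 2.0 g/L". The second is bleeding "leading to transfusion of at least 2 U of blood or packed cells". The third is symptomatic bleeding at a critical site, and gastrointestinal bleeding is on that list. The same cell defines life-threatening bleeding, again by any one criterion. There "reduction in hemoglobin level of at least 5.0 g/L" stands beside a transfusion of four units, hypotension needing intravenous inotropes, and surgery.

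Section 10.1, repeated in Section 13.2, makes a "major hemorrhagic complication (major bleeding) during the 12-month Evaluation Period" part of the primary composite. Section 13.7.2.1 defines minor bleeds, a secondary endpoint, as "clinical bleeds that do not fulfill the criteria for major bleeds". No other section states a haemoglobin threshold or its unit.

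**The concern.** The printed limits are out of scale with the criteria beside them. A fall of 0.2 g/dL is the kind of difference two samples from a stable patient can show, whereas a two-unit transfusion marks a substantial bleed.

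The 2.0 g/L limit is the border between a secondary and a primary endpoint. Read literally, a trivial bleed that happens to have two haemoglobin values can become a primary event. It would then enter the Kaplan-Meier curves, the log-rank test and the Fisher test of Section 13.7.1, and the secondary endpoint of hospitalization with a major hemorrhagic event.

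The error may also be directional. Section 5.3 says: "The major risk for subjects continuing OAT during the Evaluation Period is the risk of major bleeding and hemorrhagic stroke". If minor bleeds follow the same pattern, re-labelled bleeds would gather in the OAT arm and make withdrawal look better.

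**Working it through.** **1. Unit conversion.** 1 g/dL = 10 g/L.
- As printed: 2.0 g/L = 0.2 g/dL, and 2/140 = 1.4% of a haemoglobin of 140 g/L. 5.0 g/L = 0.5 g/dL, and 5/140 = 3.6%.
- Read as g/dL: 20 g/L (20/140 = 14%) and 50 g/L (50/140 = 36%).

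**2. Scale of the sibling criteria.** The documents give no conversion from transfused units to haemoglobin. Assume 7-12 g/L per unit.
- 2 U: 2 × 7 = 14 to 2 × 12 = 24 g/L. The printed limit is 2; the g/dL reading is 20.
- 4 U: 4 × 7 = 28 to 4 × 12 = 48 g/L. The printed limit is 5; the g/dL reading is 50.

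Both printed limits are too small by roughly a factor of ten. The g/dL reading falls inside the first range and just above the second.

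**3. Chance of meeting the limit with no true change.** Assumed, not in the documents: haemoglobin (Hb) 120-160 g/L, within-person plus assay CV 1-4%. For two samples,

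P(fall ≥ d) = 1 − Φ( d / (√2 × CV × Hb) )

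| d | Hb, CV | √2 × CV × Hb | P |
|---|---|---|---|
| 2 g/L | 120, 0.01 | 1.70 | 0.119 |
| 2 g/L | 160, 0.04 | 9.05 | 0.413 |
| 20 g/L | 160, 0.04 (largest) | 9.05 | 0.0136 |

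With a true fall of exactly 2 g/L, P = 1 − Φ(0) = 0.50.

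**4. Illustration of the effect on counts.** The documents give no minor-bleed or testing rates. Suppose a bleed that is not major by site occurs in 10-20% of OAT subjects and 5% of withdrawal subjects, and 25-100% of these have paired values. With 50 per arm (Section 13.3), subjects moved into the primary endpoint = 50 × bleed rate × paired fraction × P.
- OAT: 50 × 0.10 × 0.25 × 0.119 = 0.15 to 50 × 0.20 × 1 × 0.413 = 4.1.
- Withdrawal: 50 × 0.05 × 0.25 × 0.119 = 0.07 to 50 × 0.05 × 1 × 0.413 = 1.0.
- Gap between arms: (0.10 − 0.05) × 0.25 × 0.119 = 0.15 percentage points to (0.20 − 0.05) × 1 × 0.413 = 6.2 points.
- If pairing stays at 25%, the upper figures drop to 50 × 0.20 × 0.25 × 0.413 = 1.0 OAT subject and a gap of 0.15 × 0.25 × 0.413 = 1.5 points.

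**5. Scale of genuine events.** Section 5.1 gives this background figure: "incidence rate of major hemorrhage has been found to rise from 1.5 per 100 patient-years for patients younger than 60 years to 4.2". The second rate is on the same scale and applies above age 80. Over 12 months in 50 OAT subjects that is 50 × 0.015 = 0.75 to 50 × 0.042 = 2.1 events. One or two re-labelled bleeds would be of the same order.

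**The case against.** **Intent.** No passage states the intended unit. The transfusion comparison needs an outside conversion, and it fits 50 g/L less neatly than 20 g/L. This stands: the anomaly is certain, but the replacement values are for the sponsor to confirm.

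**Reach.** Symptomatic critical-site bleeding is already major, so the limit matters only for other clinical bleeds with paired haemoglobin values. Table 3 (Section 11.4.1) schedules no haemoglobin test in either arm; its only scheduled blood test is INR, in the OAT arm. Full pairing is therefore implausible, and the upper end of the illustration should not be read as a forecast. The 5.0 g/L limit changes only a severity label, because such a fall already exceeds 2.0 g/L.

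**Noise model.** Table 2 asks for a fall associated with the bleed, and an adjudicator may decline to count noise. In real bleeds the true fall is also not zero. The counts are therefore not bounds. But a true fall as small as 2 g/L qualifies under the text.

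**Direction.** Section 5.3 speaks of major bleeding. Additional medication is at the investigator's discretion (Section 11.2.3), and Appendix A lists antiplatelet drugs, so bleeding off OAT need not be rare. The direction is plausible, not established.

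**Adjudication.** Section 15.6 says: "The GSMC is tasked with adjudicating severity and causality of adverse events". The only general severity scale is mild, moderate or severe (Section 12.3), and Section 12.5 has the sponsor forward SAEs, so a trivial bleed might not reach the committee. Nothing gives the committee another bleeding definition, so adjudication does not cure the problem.

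**Pilot status.** Section 13.3 says the study is not powered for inference. That limits the harm to the event definition and the rates reported by arm, which are nonetheless main outputs of a pilot.

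**Conclusion.** The concern holds. As printed, a primary-endpoint criterion can be met by a haemoglobin difference within ordinary measurement variation: 12-41% of sample pairs with no true change, against at most 1.4% at 20 g/L, under the assumed haemoglobin and CV ranges. The conversion and the link to the primary endpoint follow from the documents alone. That g/dL was meant is a strong inference, not a documented fact.

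The effect on counts rests wholly on assumed bleed and testing rates: 0.15-4.1 of 50 OAT subjects and 0.07-1.0 of 50 withdrawal subjects, with a gap of 0.15-6.2 points that can be near zero. The case for correction rests on the definition being wrong as written, not on those figures or on the direction of the bias.

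**What to change.** Confirm the intended unit with the sponsor and correct both haemoglobin limits in Table 2 so that they are in scale with the criteria beside them. The apparent intention is 2.0 g/dL (20 g/L) and 5.0 g/dL (50 g/L). Use the confirmed thresholds in the eCRF and in the packets sent to the Global Safety Monitoring Committee. If any bleeds have been classified under the g/L rule, re-classify them before analysis.

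The cost is a short correction to one table, carried into two sets of study materials. If the limits rise, fewer bleeds will count as primary events and more will count as minor.

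### Table 2 counts any symptomatic GI bleed as major with no severity threshold, so small GI bleeds can enter the primary composite on a par with stroke and are expected to move the estimate toward withdrawal

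*Combined protocol and SAP*

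**What the plan says.** Section 4.0, Table 2, sets the rule as "Bleeding (major) is defined by ≥ 1 of the following criteria". The three criteria are:

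- a hemoglobin fall: "Bleeding associated with reduction in hemoglobin level of at least 2.0 g/L";
- a transfusion: "leading to transfusion of at least 2 U of blood or packed cells";
- a site: "symptomatic bleeding in a critical area or organ such as intraocular, intracranial, intraspinal or intramuscular with compartment syndrome, retroperitoneal bleeding, GI bleeding", with intra-articular and pericardial bleeding completing the list.

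The site criterion asks only that the bleed be symptomatic, a word that Table 2 does not define for bleeding. Minor bleeds are what is left over: "Clinical bleeds that do not fulfill the criteria for major bleeds". A list of life-threatening criteria sits in the same row of the table, but the table does not say that meeting one of them makes a bleed major.

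Section 10.1 joins stroke with "major hemorrhagic complication (major bleeding) during the 12-month Evaluation Period" in one composite, and section 13.2 repeats it. Section 13.1 frames the objective as non-inferiority of withdrawal on the composite. Section 13.7.1 analyses time to first event by Kaplan-Meier and log-rank, and proportions by Fisher's exact test. Section 13.3 sets 50 subjects per arm and says that the pilot is not powered for inference.

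**The concern.** The other listed sites, such as intracranial, intraspinal and pericardial, are places where a small bleed can be grave. The GI tract differs: a symptomatic bleed there may be trivial or massive, and the criterion does not separate the two. A nosebleed must meet the hemoglobin or transfusion criterion to be major, while a GI bleed of the same volume qualifies by location alone.

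The effect is not expected to be neutral between arms. Section 5.3 says: "The major risk for subjects continuing OAT during the Evaluation Period is the risk of major bleeding and hemorrhagic stroke". Small GI bleeds should therefore occur more often in the control arm, where they offset strokes in the withdrawal arm within a composite meant to show that withdrawal is no worse. In a time-to-first-event analysis, a small GI bleed also displaces any later stroke in the same subject. The minor-bleed endpoint loses the same events.

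**Working it through.** The plan has no calculation on this point to reproduce: section 13.3 gives 100 subjects (50 per arm) with no event rate, margin or power. The check has two parts.

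**1. Reading the definition.** One criterion is enough; the site criterion has no blood-loss, transfusion, admission or intervention threshold; and the minor category is residual. Sections 12.5 and 15.6 give the safety committee the seriousness, severity and causality of adverse events, but not endpoint classification. Nothing lets it move a small GI bleed to minor.

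**2. Illustrating the size.**

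Inputs from section 5.1, for warfarin in AF patients generally: strokes prevented 2.7% per year (primary prevention) or 8.4% (secondary prevention); added major bleeding 1.2% per year.

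Expected events in 50 subjects followed for one year = 50 × rate:

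- strokes lost by withdrawal: 50 × 0.027 = 1.35 (or 50 × 0.084 = 4.2);
- major bleeds saved: 50 × 0.012 = 0.6;
- net against withdrawal: 2.7 − 1.2 = 1.5 points, or 0.75 events.

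Assumption, not in the documents: symptomatic GI bleeds that meet no other major criterion occur at g% per year on OAT and at g/k off OAT. The control-arm excess is g × (1 − 1/k). The composite difference, withdrawal minus control, is 1.5 − g × (1 − 1/k) points. Each cell shows the excess, then the resulting difference:

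| g (% per year on OAT) | k = 1.5 | k = 2 | k = 3 |
|---|---|---|---|
| 1 | 0.33; +1.17 | 0.50; +1.00 | 0.67; +0.83 |
| 2 | 0.67; +0.83 | 1.00; +0.50 | 1.33; +0.17 |
| 3 | 1.00; +0.50 | 1.50; 0.00 | 2.00; −0.50 |
| 5 | 1.67; −0.17 | 2.50; −1.00 | 3.33; −1.83 |
| 10 | 3.33; −1.83 | 5.00; −3.50 | 6.67; −5.17 |

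- Cancelling the net 1.5 points at k = 2 needs g = 1.5 / 0.5 = 3% per year.
- Offsetting the full 2.7 points at k = 2 needs g = 2.7 / 0.5 = 5.4% per year. At g = 2% the excess is 0.5 events, and 0.5 / 1.35 = 37% of the stroke loss.
- With the secondary-prevention figure the net is 8.4 − 1.2 = 7.2 points, above the largest excess in the table (6.67).
- The chance of at least one such bleed among 50 controls, 1 − (1 − g/100)^50, is 0.395 at 1%, 0.636 at 2% and 0.923 at 5%. One event moves an arm's proportion by 1/50 = 2 points.
- Two-sided Fisher p-values at 50 v 50: 0 v 5 events gives 0.056, 0 v 6 gives 0.027, 2 v 9 gives 0.051 and 2 v 10 gives 0.028.

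**The case against.** **Symptomatic may be read narrowly.** Table 2's only definition of the word, for AF, requires symptoms that lead the subject to seek care. A reader might infer that every trace of blood a subject notices must be recorded as a primary event. The text allows that reading but does not compel it, because the term is undefined for bleeding. Nor is the minor category closed to all GI bleeds: asymptomatic or occult ones can still enter it. It stands that a small symptomatic GI bleed can count as major and then cannot be minor.

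**The rates are assumed.** This is correct. Section 9.4 excludes bleeding abnormalities and contraindications to anticoagulation. Section 9.3 requires at least two months of prior anticoagulation. Section 11.2.3 leaves other medication to the investigator, and Appendix A lists antiplatelets, so GI bleeds will also occur off OAT. Only the between-arm difference matters, and no ratio can be taken from the documents.

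**The pilot is not powered.** Also correct, and no margin is stated. A shift of about one event will rarely decide a test. The point estimate and Kaplan-Meier curves remain exposed, and with so few events expected each misclassified one weighs heavily.

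**The hemoglobin criterion already admits small bleeds.** As printed, 2.0 g/L (0.2 g/dL) is a very small fall, so some would qualify that way. But Table 3 schedules no hemoglobin test; its only listed blood draw is INR, in the OAT arm. The site route needs no laboratory value and stays open whatever the threshold.

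**Conclusion.** The definitional fault holds on the text, and nothing elsewhere in the documents narrows it. The expected direction, toward withdrawal, follows from sections 5.3 and 13.1. It is an expectation, not a demonstrated bias.

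The size cannot be derived from the documents. The illustration (3% per year on OAT and 1.5% off cancelling a net 1.5 points) rests on those assumed rates, on full one-year follow-up, on section 5.1 rates that are not specific to patients after successful ablation, and on the cited 1.2% not already including such small bleeds. Subjects leave the study at AF recurrence (sections 9.6 and 11.3), so actual event counts would be lower.

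A reader might infer that small GI bleeds alone would hide the whole stroke cost of withdrawal. At a 2:1 ratio that needs about 5.4% per year on OAT even for the primary-prevention figure, and no combination in the table offsets the secondary-prevention figure. A reader might also infer that the trial's test result is at stake; in an unpowered study with no margin, the harm is mainly to the descriptive estimate and the curves. The definition should be changed because the change is cheap and concerns the primary endpoint.

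**What to change.** In Table 2:

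- Remove GI bleeding from the site criterion. A GI bleed is then major only if it meets the hemoglobin criterion, the transfusion criterion or a life-threatening criterion.
- State that a bleed meeting any life-threatening criterion counts as major. Otherwise a GI bleed that needs surgery or inotropes, without a qualifying hemoglobin fall or transfusion, could drop out.
- Check the 2.0 g/L hemoglobin threshold and its unit, and reconcile it with the rest of the definition. At the printed value, many GI bleeds with repeated hemoglobin measurements would return to the major category, so removing the GI entry would achieve little on its own.

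In sections 13.7.1 and 13.7.2:

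- Count other GI bleeds as minor and report them on a separate line by arm.
- Keep GI bleeds that led to admission visible by arm beside the hospitalization endpoint, which as worded covers only thromboembolic and major hemorrhagic events.
- Report stroke and major bleeding separately beside the composite.

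The cost is a short edit to Table 2, the bleeding eCRF page and a few table lines. The downside is somewhat fewer primary events: some GI bleeds that led to admission, without a qualifying hemoglobin fall or transfusion, would leave the primary endpoint. The separate lines keep them in view.
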